### 10.4. Analysis of the secondary and exploratory endpoints

Adverse events and exploratory endpoints will be reported and evaluated by descriptive statistics.

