## **6. Clinical Investigation population**

The clinical investigation will be conducted in 40 subjects enrolled in multiple clinical investigation sites. The enrolment is competitive.

To allow for statistically significant data, a minimum of 20 eligible completed subjects in multiple clinical investigation sites will be adequate for obtaining indications on the effects of repeated reuse of catheters, hence the aim for this investigation is 20-40 completers.

Considering a drop-out rate of 50 %, the total number of subjects to be enrolled must be 40.

Recruitment and discontinuation will be followed very closely, and all replacements evaluated on an ongoing basis depending on both number of discontinued subjects and the time the subjects participated in the investigation. As a minimum sponsor will make a status on the recruitment strategy every month or at least when half of the subjects have been recruited.

The aim is to keep the LPO date. If concerns of high dropout rate recruitment/retention arise and status will be discussed by sponsor.

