### 6.3. Subject withdrawal criteria

The subject is allowed to withdraw from the investigation at any time for whatever reason without any consequences for their future treatment outside the clinical investigation. The Investigator may withdraw a subject from the investigation at any time if they judge it to be the subject's interest.

The investigator must withdraw a subject from the investigation due to:

- Major noncompliance with the CIP impacting the scientific integrity of the investigation
- If subject's safety and wellbeing is compromised by further participation
- Subjects lost to follow-up. At least three documented attempts will be made to verify subjects lost to follow-up

All replacements can be made by sponsors decision and site must contact the Clinical Manager for replacement of a subject.

A subject who is withdrawn from the investigation, for any reason, will be encouraged to contact the investigator if problems arise that the subject believes are related to the clinical investigation. Subjects who have not experienced any adverse events will not be followed up.

For subjects who experience adverse events, see Section 18.1.

If a subject shows symptom(s) of UTI, as judged by the investigator, after the subject has been included in the investigation, the subject must be examined and treated according to sites standard of care or advised by investigator or GP. If antibiotic treatment is needed the subject must be withdrawn from the investigation and Termination Visit (V5) performed as soon as possible.

The subject must be advised to stop using the reusable catheter (CLINY Self-Catheterization Set) PRIOR to start of the antibiotic treatment. The subject must also be advised to save the CLINY catheter in the CLINY Self-Catheterization set and bring it to site for the Termination Visit.

The subject can return for a new scheduled visit V1 in cases where an UTI is detected after inclusion but prior to start of the test period with CLINY Self-Catheterization Set. The subject must be terminated as a screening failure and can be enrolled as a new subject when the UTI is treated, and the subject fulfils the in- and exclusion criteria.

If a subject decides to discontinue prior to day 14 on re-use catheter (day 14 counted from day of Baseline V1), a replacement of the subject must follow. All replacements of subjects must be agreed with sponsor.

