## 10. Statistical considerations

### 10.1. Statistical design, method, and analytical procedures

Baseline assessments and endpoints will be reported by descriptive statistics and/or listed. Summaries will be presented by device i.e., IC and re-use catheters and if relevant, by other grouping variables.

Descriptive statistics for continuous variables are presented with N, Mean, SD (standard deviation), Median, Min and Max, where N denotes the number of subjects contributing with non-missing data. For discrete variables, descriptive statistics are presented with N and percentage, where percentage is based on the total number of subjects/observations with non-missing data.

All statistical analysis will be performed with [REDACTED]

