### 10.2. Definition of analysis populations

Screening Failures (SF), Intention to Treat (ITT), Full Analysis Set (FAS) and Safety populations will be defined at a formal data review meeting prior to database lock. As a minimum, the data management specialist, the clinical manager, and the statistician will be involved in the classification of subjects.

Subjects not adhering to inclusion and/or exclusion criteria are considered screening failures (SF).

The Safety population will constitute all subjects enrolled i.e., subjects who have given informed consent.

The full analysis set is a modified ITT population i.e., a sub-population of the ITT population, and will constitute all subjects enrolled, who have been exposed to at least one device, with at least one endpoint recorded (data non-missing).

Individual endpoints/data points may be excluded from the analysis, even though the corresponding subject belongs to any of the pre-defined populations. Exclusion of subjects or data points must be documented.

All statistical analysis will be based on the full analysis set, whereas adverse events and device deficiencies will be assessed in the safety population.

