### 10.5. Sample size

As this is an exploratory study no formal sample size calculation has been performed.

In a previous publication results of effect were seen with 37 completers. Hence, we aim for 40 male or female IC users in this study.

Discontinued subjects will be asked for completion of Termination Visit (V5), where the subjects will be asked to state their reason for terminating the study.

If a subject decides to discontinue prior to day 14 on re-use catheter (day 14 counted from day of Baseline V1), a replacement of the subject must follow. All replacements of subjects must be agreed with sponsor.

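### With 50% drop-out allowed for, do crude adverse-event percentages in all consented subjects need an exposure-adjusted rate and a CLINY-exposed denominator?

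*Combined protocol and SAP*

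**What the plan says.** Section 10.4 gives the whole analysis of the secondary endpoint: "Adverse events and exploratory endpoints will be reported and evaluated by descriptive statistics". Section 10.1 says what this means: "For discrete variables, descriptive statistics are presented with N and percentage". It also allows listings and has summaries presented by device, with other groupings where relevant.

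Section 10.2 sets the population: "adverse events and device deficiencies will be assessed in the safety population". It defines that population by consent: "The Safety population will constitute all subjects enrolled i.e., subjects who have given informed consent". An exposure condition appears only for the full analysis set, which is not used for adverse events.

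Four other places bear on time at risk:
- Section 6: "Considering a drop-out rate of 50 %, the total number of subjects to be enrolled must be 40".
- Section 10.5 requires a replacement under the condition "If a subject decides to discontinue prior to day 14 on re-use catheter".
- Section 6.3: "If antibiotic treatment is needed the subject must be withdrawn from the investigation and Termination Visit (V5) performed as soon as possible".
- Section 5.6 counts adverse events from consent to the end of the test period. Section 7.1 places both consent and the hand-out of CLINY at the Baseline Visit (V1).

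**The concern.** The study is about reusing one catheter for up to 28 days, and its own sizing accepts that half the subjects may not finish. In a crude percentage, someone who stopped after 5 days counts as much as someone who went the full 28. If many leave early for reasons unrelated to safety, events they would have had later are never seen, and the percentage understates the 28-day risk. A reader shown only N and percentage could not tell by how much.

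The denominator raises a second, smaller worry. Someone who consents but never uses CLINY still counts. Section 6.3 describes such a route: a urinary tract infection found after inclusion but before the test period, with possible re-enrolment under a new number.

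**Working it through.** **The plan's own figure.** 20 completers with 50% drop-out: 20/(1 − 0.5) = 40. It reproduces.

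**Exposure.** Full exposure is 40 × 28 = 1120 subject-days. If 20 subjects leave on day 14 on average, it is 20 × 28 + 20 × 14 = 840, or 75%.

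**Crude percentage against 28-day risk.** The documents give no numeric event risk and no timing of drop-out. Both are assumed here: true risk p = 20%, drop-out d = 50%.

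- *Constant hazard:* L = −ln(0.8)/28 = 0.00797 per day. A leaver with exit uniform on days 0 to b has event probability q = 1 − (1 − exp(−Lb))/(Lb). For b = 28, q = 0.104, and crude = 0.5 × 0.20 + 0.5 × 0.104 = 15.2%. For b = 14, q = 0.054, and crude = 12.7%.
- *Onset uniform over the first 7 days:* a leaver's event is captured with probability 0.875 (b = 28) or 0.75 (b = 14). Crude = 0.20 × (0.5 + 0.5 × 0.875) = 18.8%, or 0.20 × (0.5 + 0.5 × 0.75) = 17.5%.
- *Exposure-based risk:* 1 − exp(−crude/(mean days/28)). Mean days are 0.5 × 28 + 0.5 × 14 = 21 for b = 28, and 0.5 × 28 + 0.5 × 7 = 17.5 for b = 14.
- *Exit caused only by the event:* crude = 20.0%, because nothing is missed. With first-week onset, mean exposure is 0.8 × 28 + 0.2 × 3.5 = 23.1 days, and the rescaled figure is 1 − exp(−0.20 × 28/23.1) = 21.5%. With a constant hazard and days counted to the first event, it is 20.0%.

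| Onset and exit (true risk 20%) | Crude | Exposure-based |
|---|---|---|
| Constant hazard, exits days 0–28 | 15.2% | 18.3% |
| Constant hazard, exits days 0–14 | 12.7% | 18.4% |
| First-week onset, exits days 0–28 | 18.8% | 22.1% |
| First-week onset, exits days 0–14 | 17.5% | 24.4% |
| Constant hazard, exit only through the event | 20.0% | 20.0% |
| First-week onset, exit only through the event | 20.0% | 21.5% |

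The exposure-based figure is nearer the truth in the first two rows. It is further away in the third, fourth and sixth, and the fifth is a tie.

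At 25% drop-out with a constant hazard, the ratio of crude to true risk (for risks of 10–40%) is 0.88–0.89 for exits over days 0–28 and 0.81–0.82 for days 0–14.

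**Precision.** Suppose 5 subjects in 40 have one infection each over 840 CLINY-days.
- Crude: 5/40 = 12.5% (exact 95% CI 4.2% to 26.8%).
- Exposure-based: 5/840 × 28 = 0.167, and 1 − exp(−0.167) = 15.4% (5.3% to 32.2%).

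The gap is 2.9 points; the crude interval is 22.6 points wide. Table 6 rates urinary tract infection as unlikely, so fewer events are plausible. With 1 or 2, crude is 2.5% or 5.0% and rescaled is 3.3% or 6.4%.

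**Denominator.** With 8 events and 1, 2 or 4 of 40 never exposed, 8/40 = 20.0% becomes 8/39 = 20.5%, 8/38 = 21.1% or 8/36 = 22.2%. Since consent and the hand-out of CLINY share a visit, the low end is the likelier.

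**What is collected.** Visits V2 to V5 record daily CLINY catheterizations and any single-use catheter use (section 7.1). V5 records the reason for early termination. The accountability log holds dates of use (section 14). Section 20 requires the report to evaluate critically all data collected.

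**The case for a change.** The strongest case for a change is that this is the only secondary endpoint, that short exposure is foreseen in the sizing, and that nothing in section 10 commits anyone to show it. A distribution of days on CLINY assumes nothing about hazards or drop-out, costs little, and is better promised before the event counts are known. The first two rows of the table also show that the shortfall could be real: 4.8 or 7.3 points at a true risk of 20%.

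Much of this stands. Section 10 is silent on exposure, and the crude percentage should not be read as the 28-day risk under full use. But the larger shortfalls need the full 50% drop-out, mostly early, unrelated to events, and with a constant hazard. The 50% is a sizing allowance, not a forecast. Replacement of early leavers would dilute the percentage further only if replacements came on top of 40. The plan does not say so, and section 5.1 gives 40 as the total included.

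The exposure-based rate is also less simple to produce than it looks. The visit questions yield recalled averages and a note of any single-use catheter use, not a count of CLINY-days, and the documents do not show whether the event form records an onset date.

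**Conclusion.** No change is needed. Events in all consented subjects, reported descriptively and/or listed, are a legitimate account of what happened under actual use. The study is single-arm and exploratory, sections 3.2 and 10.7 set no success or pass/fail criteria, and no test is planned on adverse events, so no stated conclusion depends on the choice.

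Three things could be added, and none calls for an amendment. A summary of days on CLINY beside the event table is a gap that analysts would be expected to fill from data largely in hand. A CLINY-exposed denominator gains little: about 0.5 of a point at 8 events if one subject was never exposed. An exposure-based rate is a trade-off, better than the crude figure under a constant hazard with unrelated drop-out and worse when events start early. For an infection needing antibiotics, the event itself ends exposure under section 6.3, so when that is the only cause of exit the crude figure misses nothing.

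These sizes rest on an assumed 20% risk, 50% drop-out and the stated exit patterns, since the documents supply neither event risks nor drop-out times. If actual drop-out proves heavy and early, the report should say plainly that the percentages reflect shortened use.

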### 10.5. Sample size

As this is an exploratory study no formal sample size calculation has been performed.

In a previous publication results of effect were seen with 37 completers. Hence, we aim for 40 male or female IC users in this study.

Discontinued subjects will be asked for completion of Termination Visit (V5), where the subjects will be asked to state their reason for terminating the study.

If a subject decides to discontinue prior to day 14 on re-use catheter (day 14 counted from day of Baseline V1), a replacement of the subject must follow. All replacements of subjects must be agreed with sponsor.

## 10.6. Level of significance and power

A significance level of alpha 0.05 (2-sided) will be applied.

## 10.7. Pass/fail criteria

Due to the exploratory nature of this investigation, no formal pass/fail criteria are applied. A positive as well as a negative outcome of any endpoint will provide knowledge that is useful in the further decision-making and development.

# 11. Data management

## 11.1. Data Collection in the clinical investigation

Data management and the final statistical analyses of all measurements described in this protocol are carried out by [REDACTED] Coloplast A/S.

Data will be collected through an electronic data capturing (EDC) system on electronic Case Report Form (eCRF), a secure, internet-based case report form. This system will be used to record all subject information collected in the investigation for secure data tracking and centralised data monitoring ("remote monitoring") done by monitors, as defined in the monitoring plan.

The EDC system used is [REDACTED] delivered by [REDACTED] The system is designed to be compliant with the FDA requirements of 21 CFR part 11. It is a validated data management system allowing only qualified and trained personnel to enter the system. The system has full audit trail and electronic signature.

The sponsor will be responsible for training the investigator or delegate, in completion of the eCRF.

Principal Investigator, or delegate, at the clinical site will perform primary data collection directly into the eCRF or drawn from source-document reviews. The eCRF will be completed on a continuous basis starting from the point of enrolling the subject to final follow up.

The eCRF will be completed by the investigator, or delegate, who have signed the Site Personnel Signature and Delegation List and Clinical Investigation Training Log. It will be the responsibility of the investigator to ensure that all measurements and observations are correctly noted in the eCRF.

All assessments and observations throughout the investigation for each subject must be carefully recorded in an eCRF or in a paper CRF (pCRF) during the visit or immediately after. The eCRF makes it possible to enter data right away when they are obtained. This is the preferred way of collecting data. In case this is not possible the data should be entered no later than 7 days after the visit / procedure.

Subject reported outcomes (The HR-QoL questionnaire (ISC-Q), InCaSa questionnaire, Perception Questionnaire, Preference, reason for Preference and subject dipstick diary) will be completed by the subject in paper CRF and entered in the eCRF by the site personnel.

*Data from the lab analysis will be batch uploaded into the EDC system. Adverse events should be registered following the timelines described in the Adverse Event section. In the unforeseen situation, where site cannot establish connection to the EDC system a paper CRF (pCRF) has been printed and supplied by sponsor.*

The investigator will keep a separate list of the subjects' ID numbers, names and addresses in a locked room/cabinet. Only data referred to in this clinical investigation plan will be recorded in the CRFs.

## 11.2. Database Management, Queries and Quality Control

The data management system has restricted role-based access control. The principal investigator and delegate(s) must be trained in the system prior to getting access. The training is web-based and must be completed before

access to the investigation is granted. Training will be documented in the data management system. Only the principal investigator, or delegate, will be authorised to enter data in the eCRF.

The monitor, using his/her personal login information shall verify all critical data points against the source documents and issue electronic queries for the authorised clinical site personnel to respond, as defined in the monitoring plan.

The principal investigator, using his/her personal login information shall sign each eCRF. Automated, real time access to the data enable control on study compliance and safety assessments.

A critical quality control will be performed by the sponsor's data management team and queries issued where needed. Such queries will be reviewed by the monitor and must be resolved by the site personnel.

At the end of the study a formal data review meeting will be performed before the database will be locked.

A full audit trail ensures, that each user's (site personnel, monitor, sponsor, data manager) access to and actions in the system is tracked.

The Data Management Procedures are further described in the Data Management SOPs.

### **11.3. Data retention**

The Investigator file must be archived for a minimum period of 10 years after the final clinical investigation report has been signed.

## **12. Amendments to the Clinical Investigation Plan**

No changes in the clinical investigation procedures shall be affected without mutual agreement between the principal investigator and the sponsor. The agreement of the changes must be documented by signing the corresponding clinical investigation plan amendments and registered in the Change Log.

All significant changes require notification to the EC and applicable regulatory authority. Substantial changes may require approval from the EC and applicable regulatory authority prior to implementation.

## **13. Deviations from the Clinical Investigation Plan**

Deviations to the Clinical Investigation Plan occurs when the activities during the clinical investigation do not comply with the EC approved investigation plan.

A minor deviation is defined as those that does not increase risk or decrease benefit or don't have a significant effect on the subject's rights, safety or welfare; and/or on the integrity of the data. If a deviation increases risk or decreases benefit and/or has a significant effect on the subject's rights, safety, or welfare and/or has a significant effect on the integrity of the data it is defined as a major deviation and the Investigator must inform the monitor immediately, and the monitor will report and inform the Clinical Manager or designee immediately. For this investigation, the Clinical Manager must be informed immediately by the Investigator.

The investigator is not allowed to deviate from the Clinical Investigation Plan unless, under emergency circumstances or to protect the rights, safety, and welfare of the subject(s).

For the purposes of this investigation, any variance from the protocol is considered a deviation and is to be reported.

The site will complete a deviation eCRF form for all data-related deviations and all deviations that are not related to the data (for example, an untrained nurse performing study procedures) are reported by the monitor in the Site Report – Periodic Monitoring and actions are addressed to the Investigator for completion.

If any deviations to the Clinical Investigation Plan are detected during the monitoring visit, the monitor shall ensure the site reports all deviations in the eCRF or on the Deviation log in the Investigator File. Additionally, the monitor must report any deviation noted during the visit in the Periodic Monitoring Report.

Monitor will align with data management in each investigation, how data management will be informed about all deviations.

Details about the deviation will be collected, for example:

- Site ID, Subject ID
- Deviation Date
- Date deviation was discovered
- Clear and concise description of the event
- What the deviation is related to
- Provide a reason and record the corrective action taken, including the date of the corrective action. Please note corrective action can be site was re-educated on a procedure. Ensure the corrective action is documented.
- Record the EC notification date, when applicable, and retrieve a copy of the EC Submission Letter for the TMF.

## 14. Device Accountability

All access to the investigational devices used in the clinical investigation is controlled by storage procedures and device accountability logs as described below. The investigational devices must only be used in this clinical investigation and only according to the Clinical Investigation Plan.

Sponsor keeps a device accountability log that states the physical location of all investigational devices from shipment of investigations devices to the investigational sites until return of or disposal.

The Principal Investigator or an authorized designee keeps records documenting the receipt, use and return and disposal of the investigational devices, which includes:

- Name of the product received
- Date of receipt
- Identification of each investigational product (item no./lot no)
- Number of products received
- Number of products distributed to subjects
- The expire date
- The date(s) of use
- Subject identification
- The date on which the investigational device was returned/explanted from the subject
- The date of return unused, expired or malfunctioning investigational devices or products to Sponsor

For this investigation, all returned CLINY Self-Catheterization sets to sponsor for further analysis and laboratory assessments must be documented on the device accountability with date of return.

